3 STUDY POPULATION

3.1 Inclusion Criteria

In order to participate in this study, a patient must meet all of the criteria listed in this section:

Version 09/11/2025 page 19 of 63

- 1. History of biopsy-proven adenocarcinoma of the rectum, anus or rectosigmoid junction of any stage now with recurrent disease in the pelvis.
- 2. One prior course of radiation therapy to the pelvis for rectal cancer.
- 3. ECOG performance status 0-2.
- 4. At least 18 years of age.
- 5. Women of childbearing potential and men must agree to use adequate contraception (hormonal or barrier method of birth control, abstinence) prior to study entry and for the duration of study participation. Should a woman become pregnant or suspect she is pregnant while participating in this study, she must inform her treating physician immediately.
- 6. Able to understand and willing to sign an IRB-approved written informed consent document.

3.2 Exclusion Criteria

In order to participate in this study, a patient must not meet any of the criteria listed in this section:

- 1. Patients with pre-existing radiosensitizing conditions, such as connective tissue disorders (i.e. lupus, scleroderma) and genetic mutations (i.e. ataxia-telangiectasia).
- 2. A history of other malignancy with the exception of malignancies for which all treatment was completed at least 2 years before registration and the patient has no evidence of disease, basal cell or squamous cell carcinoma of the skin that were treated with local resection only, or carcinoma *in situ* of the cervix. Patients with history of prostate cancer treated without radiotherapy and no evidence of disease are eligible.
- 3. More than one prior course of radiation to the pelvis for rectal cancer.
- 4. Prior radiation to the pelvis for disease other than rectal cancer.
- 5. Tumor in the rectum/colon requiring radiation therapy to the full circumference of the rectum/colon.
- 6. Current treatment with any investigational agents.
- 7. Uncontrolled intercurrent illness including, but not limited to, ongoing or active infection, or unstable angina pectoris.
- 8. Pregnant and/or breastfeeding. Women of childbearing potential must have a negative urine or serum pregnancy test within 14 days of study entry.

3.3 Inclusion of Women and Minorities

Both men and women and members of all races and ethnic groups are eligible for this trial.

4 REGISTRATION AND ENROLLMENT PROCEDURES

The following steps must be taken before enrolling patients to this study:

1. Registration of consented patient in the Siteman Cancer Center OnCore database

Version 09/11/2025 page 20 of 63

2. Assignment of unique patient number (UPN)

Confirmation of patient eligibilityPatients must not start any protocol intervention or procedures prior to signing of informed consent.

4.1 Registration in OnCore Database

Patient registration to the Siteman Cancer Center OnCore database must occur within one business day of the patient signing consent.

4.2 Assignment of UPN

Each patient will be identified with a unique patient number (UPN) for this study. The UPN must not include patient initials or other identifying information. All data will be recorded with this identification number on the appropriate CRFs.

4.3 Confirmation of Patient Eligibility

Patient eligibility will be confirmed using the information listed below:

- 1. Completed eligibility checklist, signed and dated by a member of the study team
- 2. Copy of appropriate source documentation confirming patient eligibility

4.4 OnCore Subject Status Definitions

Note: subject status should not be updated in OnCore until the subject is actively in that status; future dates are not allowed.

Subject Status	Definition				
Consented	Patient has signed an IRB approved consent for the trial.				
Eligible	Patient eligibility has been confirmed by Washington				
	University PI or delegate.				
Not Eligible	Patient did not meet eligibility criteria for the trial. Note that if				
_	a patient is determined to be eligible but never initiates study				
	participation, they are not considered a screen fail.				
On Study	Patient is confirmed eligible for the study and enrolled.				
On Treatment	Patient is receiving study therapy. On Treatment date should				
	be the date of the first study treatment.				
Off Treatment	Patient has discontinued study therapy. Off Treatment date				
	should be the last day any study treatment was administered.				
On Follow Up	One day post RT to one year post RT				
Off Study	Patient has fully discontinued all study procedures (including				
	any follow-up procedures and/or review of medical record for				
	outcomes data).				

Version 09/11/2025 page 21 of 63

4.5 Screen Failures

Screen failures are defined as participants who consent to participate in the clinical trial but are not subsequently enrolled in the study (status of On Study). A minimal set of screen failure information is required to ensure transparent reporting of screen failure participants, to meet the Consolidated Standards of Reporting Trials (CONSORT) publishing requirements and to respond to queries from regulatory authorities. Minimal information includes demography, screen failure details, eligibility criteria, and any serious adverse event (if applicable).

4.6 Strategies for Recruitment and Retention

The radiation therapy technology necessary to deliver this treatment regimen is only available at the main campus facility at the Center for Advanced Medicine. Follow-up can be done at the center nearest to the patient's home at our community practice sites, such as Barnes-Jewish West County Hospital, Siteman Cancer Center South County, Barnes Jewish St Peters Hospital and potentially others. This approach reduces travel and expense and improves compliance. There will be no additional expense for the patient for participating in the clinical trial.

5 TREATMENT PLAN

5.1 Hypofractionated IMPT

5.1.1 Dose, Fractionation, and Constraints

When feasible it is strongly recommended that radiotherapy begin on a Monday. It is accepted that occasional logistical delays may occur during radiotherapy treatment due to machine downtime or other issues. Radiotherapy as administered during this study may take up to 10 business days without being considered a protocol deviation. The use of Intensity Modulated Radiation Therapy (IMRT) with photon beam therapy is permitted at the discretion of the treating investigator in order to avoid extended treatment delays due to logistical reasons (e.g. machine downtime).

Radiotherapy will consist of five fractions, delivered once daily, with pencil beam scanning proton beam therapy. Treatment with passive-scatter proton beam therapy is not allowed. Single Field Optimization (Single Field Uniform Dose) plans are preferred over Multi-Field Optimization plans. Beam angles should be selected that minimize traversing bowel gas. The use of rectal balloons filled with water is optional.

The dose to the PTV will be escalated, starting from 30 Gy in 5 fx of 6 Gy/fx. Dose per fraction will be escalated in 1 Gy/fx increments. Such increments translate into

Version 09/11/2025 page 22 of 63

approximately 11 Gy₁₀ increments of BED up to a target dose of 40 Gy(RBE) in 5 fx of 8 Gy/fx for a = BED of 72 Gy₁₀.

Daily imaging with cone beam CT to verify accurate setup is mandatory. The target coverage goal is that 95% of the PTV receives at least 95% of the prescription dose while not violating OAR dose constraints and the maximum dose should be \leq 115% of the prescription dose.

5.1.2 Treatment Planning Procedures

Treatment planning will be performed on a non-contrast CT scans. CT scans with small bowel contrast and/or IV contrast are allowed, but the contrast CT scans will have to be fused to the planning non-contrast scans. Fusion of the diagnostic MRI pelvis with the simulation CT is encouraged, but not required. Diagnostic PET/CT scans are optional. Dose volume histogram (DVH) information for the target volumes, small bowel, and uninvolved colon and uninvolved rectum (defined to be large bowel outside the clinical target volumes) is mandatory. This is to assist in interpreting outcome, including morbidity. LET optimization will be encouraged in the inverse planning of IMPT when the technology becomes available.

5.1.3 Simulation Procedures/Patient Positioning

The prone position with a bowel displacement device incorporated into the immobilization cast is generally recommended as the best way to exclude small bowel from the pelvis. The exceptions would be patients unable to lay prone or morbidly obese patients whose diagnostic supine CT scans demonstrate little or no small bowel in the pelvis. Those patients with good bladder control should be treated with a full bladder to further exclude small bowel. All patients should be simulated with oral small bowel contrast.

5.1.4 Gross Tumor Volume (GTV), Clinical Target Volume (CTV), and Planning Target Volume (PTV) Definitions

GTV should include all gross recurrent disease including lymph node metastases as determined by CT, PET/CT, MRI or biopsy.

The creation of a CTV is at the discretion of the treating radiation oncologist, but generally should be minimized to only gross disease and a margin 2-5 mm to account for microscopic spread. Elective lymph nodes should not be treated.

PTV is generated by a uniform 0.5 cm expansion about CTV or GTV if no CTV was created. In order for this tight PTV margin to be used, it is required that a physician review daily setup images for each of the five fractions.

Version 09/11/2025 page 23 of 63

5.1.5 Normal Tissue Contours

Small bowel and uninvolved colon should be contoured tightly. Uninvolved colon is defined to be large bowel that lies outside the CTV. Colon that lies within the CTV (rectum and parts of the sigmoid) is a target structure, not an avoidance structure, hence its exclusion from "uninvolved colon." The CTV is NOT to be extracted from small bowel. If small bowel lies within a CTV, that WILL contribute to the small bowel dose. Since absolute rather than relative bowel volumes are to be tracked, it is not necessary to contour the entire large and small bowel, only those loops caudal to 1 cm above the most cephalad extent of PTV.

These dose constraints are a general guideline. They are soft constraints that assume that the patient's prior DICOM data is unavailable and that each listed organ received an EQD2 of 50 Gy previously. If prior DICOM data is available, then the modeled dose to the organs from the prior treatment plan would take precedence.

Tissue	Contouring Instructions	Vol (cc)	Vol Max	Max** Point
			(Gy)	Dose (Gy)
Spinal Cord	Entire bony canal including at least 1 cm superior and inferior to PTV.	<0.35 cc	10	11.5
Cauda Equina			12	14
C1-i	(typically S3).	<10	22.5	20.5
Skin	The outer 0.5 cm of the body surface anywhere within the whole-body contour.	<10 cc	22.5	28.5
Small bowel* + 5 mm	Any and all loops of small bowel as one structure within 1 cm of the PTV in any direction.	<30 cc	20	32
Uninvolved Colon* + 5 mm	One structure including wall and contents of lumen starting 1 cm superior to PTV and ending 10 cm below PTV.	<20 cc	28.5	40
Uninvolved Rectum + 5 mm	One structure including wall and contents of lumen subtracting out the GTV or CTV (if CTV is created).	<3.5 cc <20 cc <62.7%	50 32.5 16	55
Bladder wall	Contour the bladder wall and all urine ending inferiorly at the base of the prostate.	<15 cc	20	25
Ureter	Entire organ.	n/a	n/a	30 Gy
Femoral heads	Entire femoral head and proximal femur.	<10 cc	15	n/a
Penile bulb	Contour starting superiorly at the inferior aspect of the pelvic diaphragm (urethral sphincter) and extending inferiorly and anteriorly up to 3 cm	<3 cc	15	n/a

Version 09/11/2025 page 24 of 63

Sacral Plexus	Outlining the space defined medially by the	< 5 cc	12	14
	sacral foramina from S1-S3 including			
	contouring within the sacral foramina,			
	posteriorly along the limits of the true pelvis,			
	laterally to 2-3 cm lateral to the sacral			
	foramina, and anteriorly about 3-5 mm from			
	the posterior limits of the contour.			
Prostate	Entire organ	n/a	n/a	25

^{*}Avoid circumferential irradiation

5.2 Dose Escalation Schema and MTD Definition

Refer to Section 10 for a description of the TITE-CRM design and dose escalation rules as well as for the protocol definition of MTD.

5.2.1 Dose-Limiting Toxicities (DLTs)

Dose-limiting toxicities (DLTs) are defined as any toxicity listed below that occurs within 6 months from the start of treatment and is considered possibly, probably, or definitely related to proton reirradiation:

- Any grade 5 toxicities
- Any grade 4-5 GI toxicities
- Bowel obstruction
- Grade 3-5
 - o Diarrhea
 - o Anal, colonic, or bowel ulcers
 - o Bladder perforation
 - Any fistula formation
 - o Peripheral/motor sensatory neuropathy of the pelvis above baseline
 - Osteonecrosis/soft tissue necrosis
 - Radiation dermatitis
 - Hematuria
 - o Hematochezia
 - o Bowel/pelvic hemorrhage
 - Reproductive tract toxicity

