3	5	8	40	72.00	60.00

Note – the first 6 evaluable patients enrolled will be treated at Dose Level 1 Please refer to section 10.0

Version 09/11/2025 page 10 of 63

SCHEDULE OF ACTIVITIES

	Screening	Pre- treatment ⁸	Radiation	1-2 Weeks post RT	6-8 Weeks post RT	3 Mo post RT ¹	6 Mo post RT ¹	9 Mo post RT ¹	12 Mo post RT ¹	
Informed consent	X^2									
H&P / PS / weight / DRE ¹³	X^2		X^3	X	X	X	X	X	X	
MRI pelvis ⁴	X^2				X	5	X	X	X	
CT chest / abdomen / pelvis with contrast ⁶	X^2				X ⁶		X	X	X	
Endoscopy ⁷	X^2				X	15				
OPTIONAL biopsy	$X^{2, 15}$				Х	ζ				
CBC w/diff	X^2	X^2			X^9		X			
CMP	X^2	\mathbf{X}^2			X^9		X			
CEA		X			X^9		X			
SCCA		X			X ⁹		X			
CRP		X			X ⁹		X			
LDH		X			X ⁹		X			
Pregnancy test	$X^{10,11}$									
Radiation therapy			X^{12}							
EORTC QLQ-C30		X		X		X	X	X	X	
EORTC QLQ-C29		X		X		X	X	X	X	
Adverse events		X	X^3	X	X	X	X	X	X	

- 1. +/- 2 weeks
- 2. No more than 60 days prior to registration. Screening and baseline labs can be the same draw provided the timing aligns.
- 3. Performed once during radiation therapy.
- 4. Cross-sectional imaging with either MRI or CT is acceptable.
- 5. MRI pelvis and CT chest/abdomen with contrast may be obtained 6 weeks to 3 months after radiation completion with a RECIST read at 3 months only.
- 6. If PET/CT scan is done, then CT chest/abdomen/pelvis not required.
- 7. Endoscopy with colonoscopy, sigmoidoscopy, or proctoscopy will be performed if feasible after screening.
- 8. Baseline labs and QOL assessments should be performed within 30 days of radiation therapy.
- 9. Labs should be drawn once 6 weeks to 3 months after radiation completion but should be drawn before surgery if the patient undergoes salvage surgery.
- 10. Mandatory for women of childbearing potential.
- 11. Within 14 days of registration.
- 12. 5 fractions over 1 week.
- 13. DRE only to be done if feasible.15. OPTIONAL endoscopy with biopsy performed 6 weeks to 3 months after completion of RT; for research purposes only.
- 15. OPTIONAL screening biopsy to be performed at time of baseline SOC endoscopy.

Version 09/11/2025 page 11 of 63

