5.3.4 Post-Radiation Evaluations

All patients will be followed from time of enrollment until 1 year post radiation Mandatory follow-up time points are as below. In the event that an in-person evaluation is not possible, or if not indicated by the treating investigator, a telehealth visit may be performed in its place.

- 1-2 weeks post-RT
- 6-8 weeks post-RT
- 3 months post-RT (+-/- 2 weeks)
- 6 months post-RT (+/- 2 weeks)
- 9 months post-RT (+/- 2 weeks)
- 12 months post-RT (+/- 2 weeks)

Version 09/11/2025 page 26 of 63

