5.3.4.1 Treatment Response Assessment

The following assessments should be performed 6 weeks to 3 months after radiation (but should be completed before surgery if the patient will be undergoing salvage surgery) and again 6 months after radiation:

- MRI pelvis
- CT chest/abdomen with contrast (if a PET is performed, a CT is not required)
- CBC with differential and CMP
- Study labs (CEA, SCCA, CRP, LDH)

In addition, MRI pelvis and CT chest/abdomen with contrast should be performed at 9 and 12 months after radiation. Endoscopies are optional after radiation therapy.

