5.4 Definitions of Evaluability

Endpoint	In order to be evaluable for this endpoint, a		
	patient must		
	Have received at least one fraction of study		
	radiation. Patients will be evaluated for DLTs		
Maximum tolerated dose	from the start of treatment through 6 months		
	after the start of treatment. DLT is defined in		
	Section 5.2.1.		
Clinical complete response rate.	Have received at least one fraction of study		
	radiation and undergone response assessment by		
	DRE, endoscopy, and/or cross-sectional		
	imaging.		
Freedom from locoregional	Have received at least one fraction of study		
progression (FFLP) at 12 months.	radiation and undergone response assessment.		
Overall survival at 12 months.	Have received at least one fraction of study		
	radiation		
Progression-free survival at 12	Have received at least one fraction of study		
months.	radiation and undergone response assessment.		

Version 09/11/2025 page 27 of 63

Patient reported quality of life.	Have completed the EORTC QLQ-C30 and/or QLQ-CR29 QOLs at pre-treatment and a minimum of one post-treatment time point
Toxicity	Have received at least one fraction of study radiation. Patients are evaluated from first receiving study radiation until 12 months after the conclusion of radiation.
Association of pre-treatment SCCA and post-treatment SCCA with PFS and OS at 6 months.	Have had blood drawn for SCCA at screening and after completion of study radiation
Levels of serum inflammatory markers.	Have had blood drawn for CRP and LDH after completion of study radiation

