7 DATA SUBMISSION SCHEDULE

Case report forms with appropriate source documentation will be completed according to the schedule listed in this section.

Case Report Form	Submission Schedule
On-Study Form Medical History Form	Prior to starting treatment
Treatment Summary Form	End of treatment
DLT Form	6 months post-treatment
PRO Form	Prior to starting treatment, 1-2 weeks post-treatment, 3 months post-treatment, 6 months post-treatment, 9 months post-treatment, 12 months post-treatment
Toxicity Form	Continuous
Follow Up Form	1-2 weeks post-treatment, 6-8 weeks post-treatment, 3 months post-treatment, 6 months post-treatment, 9 months post-treatment, 12 months post-treatment
Tumor Measurement Form	Baseline, 6-8 weeks post-treatment OR 3 months post-treatment
Progression Form	Time of disease progression
Death Form	Time of death
MedWatch Form	See Section 6.0 for reporting requirements

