10.1.2 TITE-CRM design

The starting dose can have a large impact on the properties of the design. After the trial is completed, most information about the MTD will be obtained if many patients are treated at or near the MTD. Thus, the sooner the choice of dose can converge on the MTD the more effective the trial will be. However, due to the uncertainty of the MTD in the reirradiation of locoregionally recurrent rectal cancer, we will start at the two dose levels lower than the expected MTD to prioritize safety. Therefore, our starting dose for this trial will be PTV total dose of 30 Gy.

The next thing to be considered is the dose escalation rules. For this trial, we will only allow a single dose level escalation per new patient enrolled on the trial.

Version 09/11/2025 page 40 of 63

Therefore, if the previous patient was treated at dose level, d_k , then a new patient can only be treated at dose levels d_{k+1} or lower. In order to determine at which level to treat the new patient, we will use a weighted, cumulative time of exposure approach.

The total length of follow-up for DLT for any patient is 6 months from the start of radiation therapy. In order to efficiently and effectively determine the MTD, we allow for a dose change when the cumulative time of exposure is 6 months. Additionally, since previously published data shows that most toxic events occur within the first 6 months from start of treatment, we also implement a linear weighting function wherein the first 6 months accounts for 75% of the follow-up where the last 3 months attributes 25% of the follow-up information. The dose for the next patient is selected so that the estimated probability at that dose is close to the target level.

A feature of the dose escalation part of the TITE-CRM program is the flexibility in specifying the margin for the dose selection. This allows the selection of the dose level for the next patient that may have an estimated probability of toxicity larger than the target level but less than the target level plus the margin. It finds the dose closest to the target probability even if it has a higher estimated probability. For this trial we set the admissible margin to be 5%, therefore, the MTD will be chosen as the dose that yields a posterior toxicity estimate closest to 35% while being between 30% and 40%. The admissible margin is also used to help determine stopping rules for the trial.

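### The DLT window is timed from the start of radiotherapy but its closing visit, imaging and form from the end, so the closing assessment usually falls after the window, with no rule for dating onset

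*Combined protocol and SAP*

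**What the plan says.** **Timed from the start of radiotherapy.** The DLT definition in section 5.2.1 covers "any toxicity listed below that occurs within 6 months from the start of treatment". Evaluability for the MTD in section 5.4 runs "from the start of treatment through 6 months" after that start. Section 10.1.2 says: "The total length of follow-up for DLT for any patient is 6 months from the start of radiation therapy".

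**Timed from the end of radiotherapy.** Section 5.3.4 lists the visit as "6 months post-RT (+/- 2 weeks". Section 5.3.4.1 schedules imaging and laboratory tests at 6 weeks to 3 months "and again 6 months after radiation". Section 7 makes the DLT Form due "6 months post-treatment".

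**Length of the course.** The Schedule of Activities footnote gives "5 fractions over 1 week". Section 5.1.1 prefers a Monday start and says the course "may take up to 10 business days without being considered a protocol deviation".

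**Use in the dose-finding model.** Section 10.1.1 ends a patient's observation at a DLT or, without one, after a fixed time T. Under section 10.2.1 the statistician updates every patient's follow-up and assigns a dose each time a new patient enrols. The same section allows observation to be prolonged after a treatment delay. Sections 10.1.2 and 10.2.1 give 75% of the weight to the first 6 months and 25% to the last 3 months.

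No section says how to date the onset of a finding first seen at the closing assessment.

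**The concern.** The two clocks differ by the length of the course, and the visit tolerance widens the difference on the late side. The assessment that would ordinarily confirm a patient as DLT-free is due after the period it is meant to close.

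Two consequences follow. First, with T read as 6 months, a patient can reach full DLT-free weight, and so influence the next dose assignment, before the closing examination and MRI. Second, several listed DLTs (ulcer, fistula, osteonecrosis or soft-tissue necrosis) may first come to light on examination or imaging. If such a finding is dated to the day it was found, it falls outside the window; if it is dated back by judgement, it falls inside. The primary endpoint should not turn on an unwritten choice. Where the choice has an effect, it can only remove events, which lowers the estimated DLT rate and favours a higher selected level.

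**Working it through.** The plan gives no figure to reproduce here; the check is calendar arithmetic plus two illustrations.

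**1. Lag of the nominal closing visit.** Inputs: course length from section 5.1.1 and the Schedule of Activities, visit anchor from section 5.3.4, window anchor from section 5.2.1.

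- Window closes at start + 6 months. Nominal visit = end of radiotherapy + 6 months. The lag is the time from first to last fraction.
- Monday to Friday: last fraction on day 4, so lag 4 days. Permitted visits run from 4 − 14 = −10 to 4 + 14 = +18 days around the close.
- Monday start over 10 business days: last fraction on day 11, so lag 11 days. Permitted visits run from −3 to +25 days.
- Over actual 2025 start dates, unequal month lengths make the Monday-start lag 3 to 5 days and 8 to 14 days respectively.

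**2. Share of closing visits after the close.** The distribution of visits within the tolerance is not in the documents. Assuming an even spread over 28 days, share = (14 + lag)/28:

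| Course (Monday start) | Even spread | Normal, SD 7 days | Triangular |
|---|---|---|---|
| 5 business days | 18/28 = 64% | 72% | 75% |
| 10 business days | 25/28 = 89% | 94% | 98% |

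Under the even spread, 20 × 18/28 = 12.9 to 20 × 25/28 = 17.9 of 20 closing visits would be late. Aligning the anchor alone (lag 0) still leaves 14/28 = 50% late, so the tolerance matters as well as the anchor.

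**3. How many onsets could lie in the gap.** Illustrative assumption: constant hazard with 35% DLT over 182 days. Then λ = −ln(0.65)/182 = 0.00237 per day, and the added probability over a gap of g days is 0.65 × (1 − exp(−λg)).

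| Gap (days) | Added DLT probability | Patients of 20 |
|---|---|---|
| 4 | 0.6% | 0.12 |
| 11 | 1.7% | 0.33 |
| 18 | 2.7% | 0.54 |
| 25 | 3.7% | 0.75 |

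These are onsets after the close. Events that began inside the window but were dated to a late discovery come on top, and the documents give no basis for counting them.

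**4. Whether one event can matter.** Power model p^exp(a), with the initial values from the section 10.2 table (0.25, 0.30, 0.35, 0.40). The prior is not stated, so several were tried. The data are a chosen scenario: Level 1, 1 DLT in 6; Level 2, 0 in 1; Level 3, 4 or 3 DLTs in 4, all with full weight. The selected level is the one whose posterior mean is nearest 35%.

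| Prior on a | Selected, 4 DLTs | Selected, 3 DLTs | Fall in posterior means |
|---|---|---|---|
| Normal, SD 0.5 | Level 1 (36.9%) | Level 2 (36.6%) | about 5 points |
| Normal, SD 0.8 | Level −1 (34.5%) | Level 1 (32.7%) | about 7 points |
| Normal, SD 1.0 | Level −1 (35.4%) | Level 1 (33.0%) | about 7 points |
| Normal, SD 1.16 | Level −1 (35.9%) | Level 1 (33.1%) | about 7.5 points |

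Removing one DLT raises the selected level by one under each prior.

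**The case against.** A reader might infer that DLTs first found at the 6-month visit are not counted. The documents do not say that. Section 5.2.1 tests when a toxicity happens, not when it is detected, so an event with onset inside the window and found days later meets the definition, and one with onset after the close is excluded by design. The DLT Form falls due after the window shuts and can cover all of it. Section 6 tracks adverse events to 12 months after radiotherapy. This objection stands; what remains is the missing dating rule.

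A reader might also blame the mismatch for the lack of a scheduled examination between months 3 and 6. That gap comes from quarterly visits and would persist with perfectly aligned anchors.

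Other surveillance exists: earlier evaluation for symptoms (section 5.3.4.2), phone calls and record review (section 5.8) and monthly review of patient data by the principal investigator (section 9). Most listed DLTs must be grade 3 or higher and would often cause symptoms. This limits the risk but does not remove it, since none of these is a scheduled examination or scan, telehealth may replace a visit (section 5.3.4), and endoscopy after radiotherapy is optional (section 5.3.4.1).

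The 89% figure rests on a 10-business-day course, and section 10.2.1 says treatment delays will be accounted for. That clause may soften the upper figure, but it does not address the ordinary visit tolerance or the 4-day lag of an undelayed course.

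Finally, sensitivity to a single event is a property of any small CRM, and the scenario above needs 3 or 4 DLTs among 4 patients at Level 3. It shows what is possible, not an average effect.

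**Conclusion.** The anchor mismatch is in the text and needs no assumption: the nominal closing visit is due 4 to 11 days after the window closes. That most closing visits fall late (64% to 89%) rests on an even spread over the tolerance; sites that book early could bring visits inside the window, but nothing requires it.

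The likely effect on the primary endpoint is small: about 0.1 to 0.7 onsets of 20 in the gap under a constant hazard, plus an unknown number of earlier onsets dated to discovery. A material upward bias in the MTD is a tempting reading, but it is not shown. What is shown is a one-directional ascertainment risk in a design where one event can move the selected level.

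The statement that patients reach full weight before the closing examination depends on reading T as 6 months. The 75%/25% weighting implies 6 + 3 = 9 months, under which a patient holds 75% of the weight at month 6. That conflict with the 6-month window is part of the same problem and must be reconciled with it.

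Severity: minor to moderate.

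**What to change.** - Put the DLT period and its closing assessment on one anchor, and reconcile the Protocol Summary and sections 2, 5.2.1, 5.3.4, 5.3.4.1, 5.4, 7, 10.1.2 and 10.2.1 accordingly.
- Set the TITE-CRM observation time T to one fixed length for all patients, not to each patient's actual visit date, closing no earlier than the last allowed date of the 6-month post-radiotherapy assessment. For a Monday start over 10 business days that is nominally 11 + 14 = 25 days beyond 6 months from the start. On 2025 calendars it reaches 28 days, or 30 days if any weekday start is allowed. No in-tolerance closing visit then falls outside the window.
- State that onset, not discovery date, decides DLT status, and that a finding first seen at the closing assessment counts unless onset is shown to be after the window.
- Match the weight function to T, replacing the present split into a first 6 and a last 3 months.
- Rerun the section 10.2 simulations under the reconciled T and weights.

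**Cost:** no new visit or scan. The DLT period becomes up to about 4 weeks longer, the observed DLT rate may be slightly higher, and the simulations must be rerun.
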